16.3 PI Time devoted to conducting the research

Describe how the PI will ensure that a sufficient amount of time will be devoted to conducting and completing the research. Please consider outside responsibilities as well as other on-going research for which the PI is responsible.

[name] has 5% of his time protected by the Department of Kinesiology for the purpose of performing this research study. [name] has 5% of her time protected by the Department of Kinesiology for the purpose of performing this research study. Sufficient study personnel and resources exist to facilitate the completion of the study when he must be absent.

16.4 Availability of medical or psychological resources

Describe the availability of medical or psychological resources that subject might need as a result of their participation in the study, if applicable.

Participants will be monitored for the duration of the protocol by study personnel. There is an AED in Noll Lab. In any emergency, 911 will be called immediately.

16.5 Process for informing Study Team

Describe the training plans to ensure members of the research team are informed about the protocol and their duties, if applicable.

The investigator and research team members involved in the study have completed their required Collaborative IRB Training Initiative (CITI) in the protection of Human Research Subjects. Study staff delegated to conduct specific study procedures will be trained on these procedures individually or in a group format by the PIs.

17.0 Other Approvals

17.1 Other Approvals from External Entities

Describe any approvals that will be obtained prior to commencing the research (e.g., from cooperating institutions, community leaders, schools, external sites, funding agencies).

We have prepared an IND application to the FDA that includes all drugs used with microdialysis in this research. This application was submitted 12/14/18. We are waiting for the FDA to assign an IND number. We will add the number to CATS when we receive it.

17.2 Internal PSU Committee Approvals

Check all that apply:

Anatomic Pathology – Hershey only – Research involves the collection of tissues or use of pathologic specimens. Upload a copy of HRP-902 - Human Tissue For Research Form on the “Supporting Documents” page in CATS IRB. This form is available in the CATS IRB Library.

Animal Care and Use – All campuses – Human research involves animals and humans or the use of human tissues in animals

Biosafety – All campuses – Research involves biohazardous materials (human biological specimens in a PSU research lab, biological toxins, carcinogens, infectious agents, recombinant viruses or DNA or gene therapy).

Clinical Laboratories – Hershey only – Collection, processing and/or storage of extra tubes of body fluid specimens for research purposes by the Clinical Laboratories; and/or use of body fluids that had been collected for clinical purposes, but are no longer needed for clinical use. Upload a copy of HRP-901 - Human Body Fluids for Research Form on the “Supporting Documents” page in CATS IRB. This form is available in the CATS IRB Library.

Clinical Research Center (CRC) Advisory Committee– All campuses – Research involves the use of CRC services in any way.

Conflict of Interest Review – All campuses – Research has one or more of study team members indicated as having a financial interest.

Radiation Safety – Hershey only – Research involves research-related radiation procedures. All research involving radiation procedures (standard of care and/or research-related) must upload a copy of HRP-903 - Radiation Review Form on the “Supporting Documents” page in CATS IRB. This form is available in the CATS IRB Library.

IND/IDE Audit – All campuses – Research in which the PSU researcher holds the IND or IDE or intends to hold the IND or IDE.

Scientific Review – Hershey only – All investigator-written research studies requiring review by the convened IRB must provide documentation of scientific review with the IRB submission. The scientific review requirement may be fulfilled by one of the following: (1) external peer-review process; (2) department/institute scientific review committee; or (3) scientific review by the Clinical Research Center Advisory committee. NOTE: Review by the Penn State Hershey Cancer Institute Scientific Review Committee is required if the study involves cancer prevention studies or cancer patients, records and/or tissues. For more information about this requirement see the IRB website at: <http://www.pennstatehershey.org/web/irb/home/resources/investigator>

18.0 Multi-Site Research

If this is a multi-site study (i.e., the study will be conducted at other institutions each with its own principal investigator) and you are the lead investigator, describe the processes to ensure communication among sites in the sections below.

18.1 Communication Plans

Describe the plan for regular communication between the overall study director and the other sites to ensure that all sites have the most current version of the protocol, consent document, etc. Describe the process to ensure all modifications have been communicated to sites. Describe the process to ensure that all required approvals have been obtained at each site (including approval by the site’s IRB of record). Describe the process for communication of problems with the research, interim results and closure of the study.

Not applicable.

18.2 Data Submission and Security Plan

Describe the process and schedule for data submission and provide the data security plan for data collected from other sites. Describe the process to ensure all engaged participating sites will safeguard data as required by local information security policies.

Not applicable.

18.3 Subject Enrollment

Describe the procedures for coordination of subject enrollment and randomization for the overall project.

Not applicable.

18.4 Reporting of Adverse Events and New Information

Describe how adverse events and other information will be reported from the clinical sites to the overall study director. Provide the timeframe for this reporting.

Not applicable.

18.5 Audit and Monitoring Plans

Describe the process to ensure all local site investigators conduct the study appropriately. Describe any on-site auditing and monitoring plans for the study.

Not applicable.

19.0 Adverse Event Reporting

19.1 Adverse Event Definitions

For drug studies, incorporate the following definitions into the below responses, as written:	
Adverse event	Any untoward medical occurrence associated with the use of the drug in humans, whether or not considered drug related
Adverse reaction	Any adverse event caused by a drug
Suspected adverse reaction	Any adverse event for which there is a reasonable possibility that the drug caused the adverse event. Suspected adverse reaction implies a lesser degree of certainty about causality than “adverse reaction”. 
• Reasonable possibility. For the purpose of IND safety reporting, “reasonable possibility” means there is evidence to suggest a causal relationship between the drug and the adverse event.
Serious adverse event or Serious suspected adverse reaction	Serious adverse event or Serious suspected adverse reaction: An adverse event or suspected adverse reaction that in the view of either the investigator or sponsor, it results in any of the following outcomes: Death, a life-threatening adverse event, inpatient hospitalization or prolongation of existing hospitalization, a persistent or significant incapacity or substantial disruption of the ability to conduct normal life functions, or a congenital anomaly/birth defect. Important medical events that may not result in death, be life-threatening, or require hospitalization may be considered serious when, based upon appropriate medical judgment, they may jeopardize the patient or subject and may require medical or surgical intervention to prevent one of the outcomes listed in this definition.
Life-threatening adverse event or	An adverse event or suspected adverse reaction is considered “life-threatening” if, in the view of either the Investigator (i.e., the study site

life-threatening suspected adverse reaction	principal investigator) or Sponsor, its occurrence places the patient or research subject at immediate risk of death. It does not include an adverse event or suspected adverse reaction that had it occurred in a more severe form, might have caused death.
Unexpected adverse event or Unexpected suspected adverse reaction.	An adverse event or suspected adverse reaction is considered “unexpected” if it is not listed in the investigator brochure, general investigational plan, clinical protocol, or elsewhere in the current IND application; or is not listed at the specificity or severity that has been previously observed and/or specified.

For device studies, incorporate the following definitions into the below responses, as written:	
Unanticipated adverse device effect	Any serious adverse effect on health or safety or any life-threatening problem or death caused by, or associated with, a device, if that effect, problem, or death was not previously identified in nature, severity, or degree of incidence in the investigational plan or IDE application (including a supplementary plan or application), or any other unanticipated serious problem associated with a device that relates to the rights, safety, or welfare of subjects.

19.2 Recording of Adverse Events

Address the frequency and process for eliciting adverse event information from research subject, e.g., “Research subjects will be routinely questioned about adverse events at study visits.”

In the response, incorporate the following as written:

All adverse events (serious or non-serious) and abnormal test findings observed or reported to study team believed to be associated with the study drug(s) or device(s) will be followed until the event (or its sequelae) or the abnormal test finding resolves or stabilizes at a level acceptable to the investigator.

An abnormal test finding will be classified as an adverse event if one or more of the following criteria are met:

- The test finding is accompanied by clinical symptoms
- The test finding necessitates additional diagnostic evaluation(s) or medical/surgical intervention; including significant additional concomitant drug treatment or other therapy
NOTE: Simply repeating a test finding, in the absence of any of the other listed criteria, does not constitute an adverse event.
- The test finding leads to a change in study drug dosing or discontinuation of subject participation in the clinical research study
- The test finding is considered an adverse event by the investigator.

Research subjects will be routinely questioned about adverse events (e.g., musculoskeletal injuries, cardiovascular events) at study visits and monitored carefully during laboratory procedures.

In the case of untoward events, those lab members present during the event are included in a debriefing and notes of the meeting are taken. The participant involved in an untoward event is interviewed in person or via telephone concerning the event and the responses are included into the notes for that event.

All adverse events (serious or non-serious) and abnormal test findings observed or reported to study team believed to be associated with the study drug(s) or device(s) will be followed until the event (or its sequelae) or the abnormal test finding resolves or stabilizes at a level acceptable to the investigator.

An abnormal test finding will be classified as an adverse event if one or more of the following criteria are met:

- The test finding is accompanied by clinical symptoms
- The test finding necessitates additional diagnostic evaluation(s) or medical/surgical intervention; including significant additional concomitant drug treatment or other therapy

NOTE: Simply repeating a test finding, in the absence of any of the other listed criteria, does not constitute an adverse event.

- The test finding leads to a change in study drug dosing or discontinuation of subject participation in the clinical research study
- The test finding is considered an adverse event by the investigator.

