The nurse draws about 30 ml (2 Tbsp) of blood from a vein in the subject's arm. We send the blood to labs for some analyses. If the subject takes thyroid hormone, we draw an extra 3.5 ml (0.2 Tbsp) to check the level of thyroid hormone. Screening tests performed on blood: CBC, Lipid panel, and blood chemistry, Interleukin Panel (IL), folic acid and B12, homocysteine, oxidized LDL, total antioxidant capacity. We do not perform genetic analyses on the blood nor look for presence of disease (e.g. HIV).

Macrovascular Function: Flow Mediated Dilation (FMD)

FMD is an assessment of conduit vessel endothelial function. A blood pressure cuff is placed on the forearm, gel on the upper arm just above the elbow, and a Doppler ultrasound probe on the gel. The ultrasound measures vessel size and blood velocity. After a 3-minute "resting" measurement, we inflate the cuff for 5 minutes to occlude forearm blood flow. After deflating the cuff, we perform a second reading.

Microvascular Function: Microdialysis (MD)

The MD experiment directly quantifies nitric oxide-mediated vasodilation in the microcirculation. Subjects undergo MD at baseline. They repeat MD 3 and 6 months after the baseline experiment.

Preparation for all MD experiments:

Women of childbearing potential undergo a urine pregnancy test.

The participant washes a ventral forearm with antimicrobial soap.

The participant washes a ventral forearm with antimicrobial soap.

Microdialysis probe insertion:

A tight band is placed around the participant's arm to visualize veins.

For each MD site, a pair of pen-marks is made on the arm 2.5 cm (1 inch) apart and away from veins. The tight band is removed. The MD tubing enters and exits the skin at the marks.

The participant's ventral forearm is cleaned with povidone iodine and alcohol, and an ice bag is placed on the arm for 5 minutes to numb the skin. Then a thin needle is inserted into the skin at each entry mark. The needle's tip travels between the layers of skin for 2.5 cm (1 inch) and exits the skin at the matching exit mark. The MD tubing is threaded through the needle, and then the needle is withdrawn leaving the tubing in the skin. Any hyperemia related to the insertion subsides in about 60 minutes.

We place a cuff on the upper arm sans the MD probes to measure BP.

We apply a local skin heater and laser Doppler probe over each MD site.

We measure local skin temperature and skin blood flow (SkBF) throughout the MD experiments.

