7.2.4 Lab Visit 2 (Month 3)

Three months following the baseline visit, participants will be asked to return to the lab to repeat measures taken during the baseline assessment. The researcher will remove the HeartPhone app from the participant's phone. Participants will be set up with an Actigraph accelerometer and given a 1-week wear log to record their activity for one week. Participants will then mail the accelerometer back at the end of the week.

A modification is proposed to include additional questions in the questionnaire pertaining to the acceptability of the Heartphone app. We will also engage in a brief semi-structured interview with the participants at this time to further gauge their experience using the HeartPhone app. The additional questions to be included in the questionnaire and semi-structured interview guide have been uploaded in the Other Attachments section of the Local Site Documents.

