7.2.5 Lab Visit 3 (Month 6)

Participants will then be asked to come back into the lab one final time approximately 6 months following their initial baseline visit. All measures taken at baseline and 3 months will again be taken at 6 months.

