9.1.1.1 Use of Codes, Master List

If identifiers will be associated with the data and/or specimens (as indicated in section 9.1.1 above), describe whether a master record or list containing a code (i.e., code number, pseudonyms) will be used to separate the data collected from identifiable information, where that master code list will be stored, who will have access to the master code list, and when it will be destroyed.

If identifiers are included or associated with the data as described in section 9.1.1 above, but no master record or list containing a code will be used, it will be assumed by the IRB that the investigator plans to directly link the identifiers with the data.

Alphanumeric codes matching the lab-generated email accounts will be used to identify participants (e.g., psuaim101). A master list containing the alphanumeric codes will be used to separate the data collected from identifiable information (the names, email addresses and phone numbers of the participants). This list that matches the names and contact information along with the code numbers will be stored in the locked file cabinet of the locked office of the research project manager (18A Rec Hall). Only the study team members responsible for consent and subject compliance monitoring calls will have access to that list. The list will be destroyed upon completion of the study.

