As with venipuncture or any event that breaks the skin, infection is possible. However, no participants in any of the researchers' experiments have reported infection. The researchers place a sterile bandage on the site after the experiment. Although rare, if the membrane should break in half during removal, the researcher removes the remaining half by gently pulling the attached tubing. This presents no additional risk to the participant. In the unlikely event in which the membrane breaks during removal leaving an isolated piece of membrane under the skin, they treat the piece of membrane in a manner similar to that for a splinter in the skin. In this case, they have to make a superficial incision for removal.

Perfusate: Lactated Ringer's solution flows through the microdialysis probes. An allergic reaction to this physiological saline solution, although possible, is highly unlikely.

All substances added to the fluid perfusing the microdialysis probes (ACh, L-NAME, SNP) have been used previously clinically and/or in research in humans.

Microdialysis delivers small amounts of the substances to a nickel-sized area of the skin. The small quantities used and the extremely localized administration during microdialysis does not produce systemic effects. There are no reports of long- or short-term side effects of these substances administered through microdialysis. The chance of adverse reactions to these substances is extremely small given the minute amount delivered to a very small area of skin, the lack of adverse reactions to similar amounts delivered via MD in many other studies, and the lack of adverse effects in human cell cultures. There is a slight chance of allergic reaction to these substances that could produce redness, itching, rash, and/or swelling. A severe reaction (anaphylactic shock) could also cause fever, difficulty in breathing, changes in pulse, convulsions, and/or loss of consciousness.

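### Adverse events are actively asked about only at study visits, so harms that appear after the last (month-6) session are captured only if volunteered, and those after earlier sessions are mostly asked about some three months later

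*Combined protocol and SAP*

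**What the plan says.** On eliciting harms, section 19.2 states: "Research subjects will be routinely questioned about adverse events (e.g., musculoskeletal injuries, cardiovascular events) at study visits and monitored carefully during laboratory procedures". It also accepts events that participants report themselves, and it provides for an interview, in person or by telephone, once an untoward event is known. It schedules no call, message or diary after a session. Sections 10.3 and 10.4, which ask for the method and frequency of safety data collection, are marked not applicable, as is section 3.3.2 on follow-up of withdrawn subjects.

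On the visits, section 7.2.4 says: "Three months following the baseline visit, participants will be asked to return to the lab to repeat measures taken during the baseline assessment". Section 7.2.5 brings participants back "come back into the lab one final time approximately 6 months following their initial baseline visit" and adds: "All measures taken at baseline and 3 months will again be taken at 6 months". For the ancillary group, section 7.2.2 says of microdialysis: "They repeat MD 3 and 6 months after the baseline experiment".

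On the harms themselves, section 11.0 says of microdialysis: "As with venipuncture or any event that breaks the skin, infection is possible". The same section lists a slight infection risk from blood draws, bruising, rash or itching from adhesive or from the perfused agents, and muscle pain or musculoskeletal injury from the exercise tests.

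**The concern.** Several of the listed harms can appear, or become apparent, only after the participant has left the laboratory. Infection at a needle site is the clearest case. Questioning at visits finds such events only if another visit follows soon enough for them to be remembered. Here the last round of invasive and exertional procedures coincides with the last visit, and the earlier rounds are about three months from the next question.

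Two things are at stake. First, the three rounds would not be comparable: two would rest on long recall and the third on volunteered reports alone, so a low count after month 6 could not be read as few harms. Second, section 17.1 says that an IND application covers the microdialysis agents, and the 15-day and 7-day reporting limits in section 19.4 run from the sponsor-investigator's receipt of the event information. An event nobody asks about may reach the team late or not at all.

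**Working it through.** The plan gives no figure of its own on this point, so the check is a count of sessions from the visit schedule.

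**Inputs**
- Main study: 30 participants; ancillary study: 10 of those 30 (8.1).
- Three time points: months 0, 3 and about 6 (7.2.2, 7.2.4, 7.2.5).
- Per time point: one blood draw and two exercise tests for everyone, and one microdialysis session for ancillary participants (7.2.2).
- Ancillary participants may do the main and ancillary procedures on separate days; order, gap and uptake are not given (7.3).

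**Sessions planned**
- Microdialysis: 10 × 3 = 30.
- Blood draws: 30 × 3 = 90.
- Exercise tests: 30 × 3 × 2 = 180.

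**Sessions with no later study visit**, under full attendance. The split-day rows assume that the second day is itself a visit at which the questions are asked.

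| Scenario | Microdialysis | Blood draws | Exercise tests |
|---|---|---|---|
| No split days | 10/30 = 33% | 30/90 = 33% | 60/180 = 33% |
| All ten split, main day first | 10/30 = 33% | (30 − 10)/90 = 22% | (60 − 20)/180 = 22% |
| All ten split, microdialysis day first | 0/30 = 0% | 30/90 = 33% | 60/180 = 33% |

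**Delay for the rest.** With no split days, the other 20 microdialysis sessions, 60 draws and 120 exercise tests are next asked about at the following time point, roughly three months on. Where a participant splits days, harms from the first day can be asked about at the second.

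**Dropout.** Each participant's last attended session has no later question, and no contact is planned after withdrawal. If 3 of 30 leave after Visit 1 (an assumption), main-study sessions number 90 − 2 × 3 = 84 and the unasked share is 30/84 = 35.7%. If 6 leave, it is 30/(90 − 2 × 6) = 30/78 = 38.5%. Both figures assume no split days.

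**Is there another active route?** The only other contact mentioned is in section 9.1.1.1: "Only the study team members responsible for consent and subject compliance monitoring calls will have access to that list". That sentence concerns access to the master list and gives the calls neither schedule nor content. Section 7.4.4 marks compliance monitoring as not applicable. Nothing links such calls to adverse events.

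**The case against.** The best case for the plan is that visit-based questioning follows the example wording in the institution's own template and is ordinary for a single-group trial of 30 people. The exercise tests are submaximal and observed. Section 11.0 places muscle pain and injury during the tests, treats bruising as common and minor, and says no participant in the researchers' experiments has reported an infection. The documents give no onset window for any of these harms, so delayed onset is partly inference. All of this stands, and it keeps the point modest. It does not remove the gap, because infection and skin reaction are listed risks and the last session has no question after it.

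Four stronger readings are tempting, and the documents do not support them.
- A reader might infer that harms after month 6 go unrecorded. They do not necessarily: volunteered reports are accepted and, if believed related to a study drug or device, followed to resolution. The consent forms were not available; an instruction there to telephone the team would help, but it would still be a passive route.
- A reader might take one third as a fixed result. It is one scenario; section 7.3 allows others.
- A reader might attach a confidence bound to a zero count and say that the trial would overstate its safety evidence. The plan promises no per-session harm rate: section 8.3 covers efficacy outcomes, and section 10.7 on safety tests is marked not applicable. Such a bound has no target.
- A reader might treat the calls in 9.1.1.1 as an existing resource. Given 7.4.4, that cannot be assumed.

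**Conclusion.** The point holds in a limited form. Active questioning is planned only at visits, so harms emerging after the month-6 session depend on the participant volunteering them, and most harms from the earlier sessions depend on recall over about three months. With full attendance and no split days, one third of each kind of session has no later question. With all ten ancillary participants splitting days, the share for a given procedure runs from 0% to 33% depending on order; with dropout and no split days it exceeds one third.

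The word only rests on the absence of any other elicitation step in the documents; section 19.2 does not itself say so. The likely harms are mostly minor and the primary endpoint is untouched. This is a cheap improvement to harm capture, not a flaw that threatens the trial's main result.

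**What to change.** In section 19.2:

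- Add a short fixed adverse-event item covering needle sites, skin reaction, muscle or joint injury, chest symptoms and medical contact to the one-week Actigraph wear log mailed back after Visit 2 (7.2.4) and after Visit 3. The Visit 3 log follows from the statement in 7.2.5 that all month-3 measures are repeated; 7.2.5 should say so outright. Where an ancillary participant splits a time point, the item should be completed after the later day.
- Define the adverse-event window as running to the return of the month-6 log.
- If procedure harms are reported per session, use the number of sessions actually followed as the denominator.

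If every log comes back, no session is left without a later question, and the three-month delay remains only for the month-0 round (10 of 30 microdialysis sessions, 30 of 90 draws, 60 of 180 exercise tests). A contact about a week after Visit 1 would close that too. It is optional and would be new work, because the accelerometer log before Visit 1 belongs to screening. Sections 9.1.1.1 and 7.4.4 should be reconciled on whether compliance calls take place.

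The cost is protocol wording and a few lines on an existing form. The downside is a few more minor events to record and assess.
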